9.2. Reporting of Adverse Events

The investigator (or physician designee) is responsible for verifying and providing source documentation for all adverse events and assigning the attribution for all adverse events for subjects enrolled.

Adverse Events that are routinely collected according to GCP shall be submitted to BMS every three (3) months by the last working day of the third month.

The Adverse Event information required to be sent to BMS is noted in an attached ‘Bristol-Myers Squibb Early Asset Investigator Sponsored Research (ISR) Import Plan’ which describes the method of collection and submission to BMS via the mailbox:

[contact]

When the file is submitted to BMS, it must be noted whether the file contains all Non Serious Adverse Events (only adverse events not previously submitted to BMS within the 3 months).

All Serious Adverse Events must be reported to BMS Worldwide Safety

It is the responsibility of the PI and the research teams to ensure serious adverse events are reported according to the Code of Federal Regulations, Good Clinical Practices, the protocol guidelines, the sponsor's guidelines, and Institutional Review Board policy.

- All Serious Adverse Events (SAEs) that occur following the subject's written consent to participate in the study through 100 days of discontinuation of dosing must be reported to BMS Worldwide Safety, whether related or not related to study drug. If applicable, SAEs must be collected that relate to any later protocol-specified procedure (eg, a follow-up skin biopsy).
- Following the subject's written consent to participate in the study, all SAEs, whether related or not related to study drug, are collected, including those thought to be associated with protocol-specified procedures. The investigator should report any SAE occurring after these aforementioned time periods, which is believed to be related to study drug or protocol-specified procedure.
- An SAE report should be completed for any event where doubt exists regarding its seriousness;
- If the investigator believes that an SAE is not related to study drug, but is potentially related to the conditions of the study (such as withdrawal of previous therapy or a complication of a study procedure), the relationship should be specified in the narrative section of the SAE Report Form.

An appropriate SAE form (e.g. ex-US = CIOMS form or USA = Medwatch form) should be used to report SAEs to BMS. If you prefer to use your own Institutional form, it must be reviewed by the BMS Protocol Manager prior to study initiation to ensure that at a minimum all of the data elements on the CIOMS form are present. Note: Please include the BMS Protocol number on the SAE form or on the cover sheet with the SAE form transmission.

- - The CIOMS form is available at: <http://www.cioms.ch/index.php/cioms-form-i>
 - The MedWatch form is available at: [MedWatch 3500 Form](#)
- The Sponsor will reconcile the clinical database AE cases (**case level only**) transmitted to BMS Global Pharmacovigilance ([contact]).
 - The Investigator will request from BMS GPV&E, [contact] the SAE reconciliation report and include the BMS protocol number every 3 months and prior to data base lock or final data summary
 - GPV&E will send the investigator the report to verify and confirm all SAEs have been transmitted to BMS GPV&E.
 - The data elements listed on the GPV&E reconciliation report will be used for case identification purposes. If the Investigator determines a case was not transmitted to BMS GPV&E, the case should be sent immediately to BMS ([contact]).
- In addition to the Sponsor Investigator's responsibility to report events to their local HA, suspected serious adverse reactions (whether expected or unexpected) shall be reported by BMS to the

relevant competent health authorities in all concerned countries according to local regulations (either as expedited and/or in aggregate reports).

- In accordance with local regulations, BMS will notify sponsor investigators of all reported SAEs that are suspected (related to the investigational product) and unexpected (ie, not previously described in the IB). An event meeting these criteria is termed a Suspected, Unexpected Serious Adverse Reaction (SUSAR). Sponsor investigator notification of these events will be in the form of either a SUSAR Report or a Semi-Annual SUSAR Report.
 - Other important findings which may be reported by BMS as an Expedited Safety Report (ESR) include: increased frequency of a clinically significant expected SAE, an SAE considered associated with study procedures that could modify the conduct of the study, lack of efficacy that poses significant hazard to study subjects, clinically significant safety finding from a nonclinical (eg, animal) study, important safety recommendations from a study data monitoring committee, or sponsor or BMS decision to end or temporarily halt a clinical study for safety reasons.

Upon receiving an ESR from BMS, the investigator must review and retain the ESR with the IB. Where required by local regulations or when there is a central IRB/IEC for the study, the sponsor will submit the ESR to the appropriate IRB/IEC. The investigator and IRB/IEC will determine if the informed consent requires revision. The investigator should also comply with the IRB/IEC procedures for reporting any other safety information.

SAEs, whether related or not related to study drug, and pregnancies must be reported to BMS within 24 hours \ 1 Business Day of becoming aware of the event. SAEs must be recorded on either CIOMS, MedWatch, or approved site SAE form.

Pregnancies must be reported and submitted to BMS. BMS will perform due diligence follow-up using the BMS Pregnancy Form which the investigator must complete.

SAE Email Address: [contact]

SAE [contact]

If only limited information is initially available, follow-up reports are required. (Note: Follow-up SAE reports should include the same investigator term(s) initially reported.)

If an ongoing SAE changes in its intensity or relationship to study drug or if new information becomes available, a follow-up SAE report should be sent within 24 hours \ 1 Business Day to BMS using the same procedure used for transmitting the initial SAE report.

All SAEs should be followed to resolution or stabilization.

The causal relationship to study drug is determined by a physician and should be used to assess all adverse events (AE). The causal relationship can be one of the following:

- Related: There is a reasonable causal relationship between study drug administration and the AE.
- Not related: There is not a reasonable causal relationship between study drug administration and the AE.

The term "reasonable causal relationship" means there is evidence to suggest a causal relationship.

Adverse events can be spontaneously reported or elicited during open-ended questioning, examination, or evaluation of a subject. (In order to prevent reporting bias, subjects should not be questioned regarding the specific occurrence of one or more AEs.)

Recommended Adverse Event Recording Guidelines

Attribution	Grade 1	Grade 2	Grade 3	Grade 4	Grade 5
Unrelated	Phase I	Phase I	Phase I Phase II Phase III	Phase I Phase II Phase III	Phase I Phase II Phase III
Unlikely	Phase I	Phase I	Phase I Phase II Phase III	Phase I Phase II Phase III	Phase I Phase II Phase III
Possible	Phase I Phase II	Phase I Phase II Phase III			
Probable	Phase I Phase II	Phase I Phase II Phase III			
Definitive	Phase I Phase II	Phase I Phase II Phase III			

10. Statistical Considerations

Data Collection

All patients who meet eligibility criteria and are enrolled in this trial will be registered in Clinical Oncology Research (CORe) Database at the University of Texas M D Anderson Cancer Center at Houston. This study will utilize CORe and Moclia as its case report forms (CRF) for data collection.

Data Protection and Confidentiality

All patients who meet eligibility criteria and are enrolled in this trial will be registered in Clinical Oncology Research Database (CORe) at the University of Texas M D Anderson Cancer Center at Houston. All protocol participants must be registered in the CORe. The date in the current informed consent document is displayed to ensure only the most current IRB approved version is used. Consent date, registration date, off study date, and evaluability data are required for all registrants.

The principal investigator agrees to keep all information and results concerning the study confidential. The confidentiality obligation applies to all personnel involved with this clinical trial. The Investigator must ensure that each participant's anonymity will be maintained in accordance with applicable laws. The principal investigator should keep a separate log of ID numbers, names and addresses. Documents that contain the names associated with these ID numbers (e.g., written consent/assent forms), should be

maintained by the Investigator in strict confidence except to the extent necessary to allow auditing by regulatory authorities, auditing or monitoring by the IRB.

The Principal Investigator shall obtain all such permissions and authorizations as may be necessary or desirable to allow the collection and use of information protected under federal privacy laws and state privacy laws, including permission/authorization for monitoring and analysis (including re-analysis in combination with results of other studies), for regulatory submission purposes and for applicable reporting (if any).

Tumor response will be determined using the Immune Related Response Criteria (irRC) as described in section 8.3.

The Investigator is responsible for completing an efficacy/safety summary report, and submitting it to the IND Office Medical Affairs and Safety Group, for review and approval. This should be submitted after the first 3 evaluable patients in groups 1 and 3 complete 29 days of study treatment, and after the first 3 evaluable patients in group 2 complete 43 days of therapy initiation, and every 3 evaluable patients per group thereafter. IND Office approval must be obtained prior to advancing/changing dose levels.

A copy of the cohort summary should be placed in the Investigator's Regulatory Binder.

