- Any clinically ≥ grade 3 non-hematologic toxicity as defined in the NCI CTC v4.0, expected and believed to be related to the combination of study drug and radiation (except nausea and vomiting, diarrhea and electrolyte imbalances responsive to appropriate regimens, alopecia or fatigue lasting less than 7 days).
- Grade 3 Febrile neutropenia
- Any grade 4 neutropenia (with or without fever and/or sepsis) or thrombocytopenia (without bleeding) lasting at least 1 week or longer (as defined by the NCI-CTC v4.0).
- Any of the Grade 4 hematologic adverse events for >7 days.
- Any ≥ grade 3 nausea or vomiting lasting > 5 days despite anti-emetics regimens or ≥ grade 3 diarrhea refractory to anti-diarrhea medications, >48 h.
- Any Grade 2 drug-related uveitis or eye pain or blurred vision that does not respond to topical therapy and does not improve to Grade 1 severity ≤2 weeks OR requires systemic treatment. Any other grade 3 non-hematologic toxicity including symptoms/signs of vascular leak or cytokine release syndrome; or any severe or life-threatening complication or abnormality not defined in the NCI-CTCAE v4.0 that is attributable to the therapy, with the following EXCEPTIONS:
 - Grade 3 or grade 4 electrolyte abnormalities that are not complicated by associated clinical adverse experiences, last ≤48 hours and either resolve spontaneously or respond to conventional medical intervention
 - Isolated Grade 3 elevation of amylase or lipase not associated with clinical or radiographic evidence of pancreatitis
 - Isolated Grade 3 fever not associated with hemodynamic compromise (eg, hypotension, clinical or laboratory evidence of impaired end-organ perfusion)

- Grade 3 endocrinopathy that is well controlled by hormone replacement
- Grade 3 tumor flare (defined as pain, irritation, or rash that localizes to sites of known or suspected tumor)
- Grade 3 fatigue for ≤ 7 days.
-

Group 2 and Group 3 definition of DLTs:

- DLTs used to define the MTD in combination with radiation section 7.1.1.2 and 7.1.1.3 will only use DLTs associated with organ toxicity for the organ irradiated.
- SBRT related adverse events: Any grade ≥ 3 events occurring in radiation volume field will be considered as DLT.
- Any \geq Grade 3 bronchospasm or other hypersensitivity reactions lasting for > 6 h;

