7.3.4. Criteria for Permanent Discontinuation of Ipilimumab/BMS-986156 or nivolumab/BMS-986156

Patients who demonstrate signs of progression of disease prior to completion of Ipilimumab/BMS-986156 or Nivolumab/BMS-986156 may continue on trial if determined to provide clinical benefit per the treating physicians and/or PI's discretion.

- Patients will continue to be monitored with visits or phone calls (if patient is unable to arrive) as discussed in section 9.1.3 but will no longer receive further treatment if:
- Patients suffer any of the following adverse events with at least a possible, probable or definite attribution to study treatments:*Adverse event(s) considered related to study treatments as described below:*
 - Any \geq Grade 2 eye pain or reduction of visual acuity that does not respond to topical therapy and does not improve to Grade 1 severity within 2 weeks of starting therapy OR requires systemic treatment;
 - Any \geq Grade 3 bronchospasm or other hypersensitivity reaction;
 - Any other \geq Grade 3 non-skin related adverse event with the exception of laboratory abnormalities;
 - Any Grade 4 laboratory abnormalities, except AST, ALT, or total bilirubin;
 - AST or ALT \geq 8 \times ULN,
 - Total bilirubin \geq 5 \times ULN;
 - Any other Grade 4 adverse event;
 - Drug related toxicity that prevents administration of ipilimumab/BMS-986156 for \geq 21 days or nivolumab/BMS-986156 for 14 days from the scheduled dose
- Any adverse event, laboratory abnormality or intercurrent illness which, in the judgment of the investigator, presents a substantial clinical risk to the subject with continued study drug dosing;
- Subject experiences an allergic/infusion reaction while receiving study drug at a slower infusion rate due to a prior allergic/infusion reaction;
- Any motor neurologic toxicity \geq Grade 3 regardless of causality;

- Any \geq Grade 3 treatment-related sensory neurologic toxicity.
- Drug related toxicity that prevents administration of ipilimumab for \geq 21 days from the scheduled dose

Exceptions to Permanent Discontinuation of ipilimumab dosing:

- Hospitalization for \leq Grade 2 adverse events where the primary reason for hospitalization is to expedite the clinical work-up;

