Not related: There is not a reasonable causal relationship between study drug administration and the AE.

The term "reasonable causal relationship" means there is evidence to suggest a causal relationship.

Adverse events can be spontaneously reported or elicited during open-ended questioning, examination, or evaluation of a subject. (In order to prevent reporting bias, subjects should not be questioned regarding the specific occurrence of one or more AEs.)

Non-serious Adverse Event

- Non-serious Adverse Events (AE) are to be provided to BMS in aggregate via interim or final study reports as specified in the agreement or, if a regulatory requirement [eg, IND US trial] as part of an annual reporting requirement.
- Non-serious AE information should also be collected from the start of a placebo lead-in period or other observational period intended to establish a baseline status for the subjects.

A ***non-serious adverse event*** is an AE not classified as serious.

Non-serious Adverse Event Collection and Reporting

The collection of non-serious AE information should begin at initiation of study drug. All non-serious adverse events (not only those deemed to be treatment-related) should be collected continuously during the treatment period and for a minimum of **100** days following the last dose of study treatment.

Non-serious AEs should be followed to resolution or stabilization, or reported as SAEs if they become serious. Follow-up is also required for non-serious AEs that cause interruption or discontinuation of study drug and for those present at the end of study treatment as appropriate.

Laboratory Test Abnormalities

All laboratory test results captured as part of the study should be recorded following institutional procedures. Test results that constitute SAEs should be documented and reported to BMS as such.

The following laboratory abnormalities should be documented and reported appropriately:

- any laboratory test result that is clinically significant or meets the definition of an SAE
- any laboratory abnormality that required the participant to have study drug discontinued or interrupted
- any laboratory abnormality that required the subject to receive specific corrective therapy.

It is expected that wherever possible, the clinical rather than laboratory term would be used by the reporting investigator (eg, anemia versus low hemoglobin value).

Potential Drug Induced Liver Injury (DILI)

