10.1.1. Safety Evaluation

The incidence of clinical and laboratory adverse events will be reported and graded according to the NCI-CTCAE version 4.0 (available at <http://ctep.cancer.gov/reporting/ctc.html>). Adverse events will be reported in frequency tables overall, by intensity, and by relationship. Laboratory values will be reported in shift tables and with summary statistics.

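### The only defined adverse-event causality scale refers to study drug, so if the 'by relationship' tables use it, SBRT-only toxicity in groups 2 and 3 is counted as not related

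*Combined protocol and SAP*

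**What the plan says.** Section 9 and Section 9.2 give the same rule: "The causal relationship to study drug is determined by a physician and should be used to assess all adverse events (AE"). The scale has two levels, Related and Not related. The second is defined as "Not related: There is not a reasonable causal relationship between study drug administration and the AE". No level or second field for radiation is described. For serious events thought to have a non-drug cause linked to the study, Section 9.2 says that "the relationship should be specified in the narrative section of the SAE Report Form".

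Section 10.1.1 then plans the output: "Adverse events will be reported in frequency tables overall, by intensity, and by relationship". It names neither the cause nor the scale.

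Other sections attribute differently. Section 7.3.2 (treatment delay) uses three degrees of relation to trial drug, with or without SBRT. Section 7.3.4 (permanent discontinuation) requires "at least a possible, probable or definite attribution to study treatments". Section 7.2.1 states for groups 2 and 3 that grade 3 or higher "events occurring in radiation volume field will be considered as DLT". It also has a criterion that depends on the event being believed related to drug and radiation together. The table in Section 9.2 headed "Recommended Adverse Event Recording Guidelines" has five attribution levels and names no cause.

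On collection, Section 9 is explicit: "All non-serious adverse events (not only those deemed to be treatment-related) should be collected continuously".

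**The concern.** Section 2.1 lists five primary objectives. One concerns the BMS-986156 dose with ipilimumab and no SBRT. The other four are the safety of ipilimumab or nivolumab plus BMS-986156 given with SBRT to liver or lung. A causality code that asks only about drug cannot separate a reaction caused by radiation from one caused by the underlying disease.

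Two uses of the data would suffer. The first is any treatment-related rate reported for groups 2 and 3. The programme's own benchmark for ipilimumab plus SBRT, in Section 3.3, is a grade 3 treatment-related rate of 34%, and a drug-only rate is not the same quantity. The second is the question of which component caused an event. Pneumonitis appears in Section 5.1.8 as a presumed immune-related event and in Section 7.5 as an acute radiation reaction. A yes/no to drug cannot show drug, SBRT or both. Attribution is also hard to rebuild reliably once the trial is over.

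**Working it through.** The plan gives no figure of its own on this point, so the check is a comparison of the texts followed by short arithmetic on size.

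**Attribution, place by place**

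| Place | Levels | Attributed to | Used for |
|---|---|---|---|
| Sections 9 and 9.2, causality text | 2, each defined | study drug | all AEs |
| Section 9.2, recording table | 5, not defined | not named | which events to record |
| Section 7.3.2 | possibly, probably, certainly | trial drug with or without SBRT | delay |
| Section 7.3.4 | possible, probable, definite | study treatments | discontinuation |
| Section 7.2.1, one criterion | believed related | drug and radiation combined | DLT |
| Section 10.1.1 | not stated | not stated | AE tables |

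Only the first row has written definitions, and only it is said to apply to every AE. It is also the row that speaks of a causal relationship; the recording table speaks of attribution. The natural reading of Section 10.1.1 is therefore the drug-only scale, but the text does not settle it. On that reading an SBRT-only event is Not related.

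**Size**

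Inputs:
- 20 patients in each of groups 2 and 3 (Section 10.2.5).
- Grade 3 or higher toxicity of 2% after liver SBRT, and toxicity of 7.9% after lung SBRT (Section 7.5, which does not state the grade for the lung figure).

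Expected SBRT-only patients = group size × rate:
- 20 × 0.02 = 0.4
- 20 × 0.079 = 1.58, about 1.6
- both groups together: 40 × 0.02 = 0.8 to 40 × 0.079 = 3.16, about 3.2

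Shift in a per-patient related rate = expected patients / group size:
- 0.4/20 = 2 points
- 1.58/20 = 7.9, about 8 points

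In whole patients, a true treatment-related count of 7/20 (35%, near the 34% benchmark) would be shown as 6/20 (30%) with one SBRT-only patient and 5/20 (25%) with two.

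This assumes that each event is judged wholly unrelated to drug and that the patient has no other drug-related event in the same table. Section 7.5 also gives 17% for central and 46% for peripheral lung lesions. That sentence calls the central rate the higher one, which contradicts its own figures, so neither was used.

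**Outputs that do not depend on drug attribution**
- The overall and by-intensity tables (Section 10.1.1).
- The between-group comparison of grade 3 or higher events, which has no relationship filter (Section 10.2.3).
- The in-field DLT criterion, which goes by location and grade (Section 7.2.1).
- SAE capture, which is regardless of relatedness (Sections 9.1 and 9.2).

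**The case against.** The strongest reply is that the primary safety results do not use this code. SBRT toxicity is counted in the overall and by-intensity tables, in the grade 3 or higher comparison and in the DLT rule, and Section 7.5 requires in-field reactions to be evaluated and graded. No section makes a treatment-related rate an endpoint, and Section 10.2.1 calls the comparisons exploratory. All of that stands, and it confines the point to results reported by relationship.

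Four stronger readings are tempting, and the documents do not support them:
- A reader might infer that SBRT toxicity will certainly be tabulated as not related. Section 10.1.1 does not name the scale, and on the five-level scale an SBRT reaction could be coded as possible or definitive.
- A reader might see a contradiction in an in-field grade 3 event being both a DLT and not related. The DLT criterion asks where and how severe; the causality code asks about drug. Both can be true of one event.
- A reader might infer that low-grade SBRT reactions need not be recorded, because the Section 9.2 table lists grade 1 and 2 unrelated or unlikely events under Phase I only. That table is only recommended, Section 9 says to collect everything, and no separate phase II part is marked out. The risk is one of ambiguity.
- A reader might put the loss at 3 of 20 patients (15 points). That is nearly double the 7.9% rate used above.

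It is also fair that the case report forms (CORe and Moclia) and the data import plan are not available here, so a radiation field may exist. The protocol simply describes none. Some in-field pneumonitis or rash would probably be coded as drug-related anyway, since Section 9 asks only for evidence suggesting a causal link. That would shrink the effect.

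**Conclusion.** The point holds in a limited form. The plan's one defined causality scale is about study drug, it applies to all adverse events, and it does not match the attributions used in Sections 7.2.1, 7.3.2 and 7.3.4 or in the recording table of Section 9.2. If the by-relationship tables use it, related-event results in groups 2 and 3 omit SBRT-only toxicity, and comparison with the 34% benchmark is not like for like.

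The expected understatement is small, about 2 to 8 points per group, under the assumptions stated with the calculation. It does not extend to the safety profile as a whole, and sample size, alpha and power are untouched. The change is still worth making before data are collected because it is cheap and the information is hard to recover later.

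**What to change.** - **Sections 9 and 9.2:** record two attributions for every adverse event, one to study drug and one to SBRT, on a single scale. State which levels count as related. Use the same terms wherever else the protocol relies on attribution, so that Sections 7.2.1, 7.3.2 and 7.3.4 can be applied from recorded data. Which events should lead to delay or discontinuation is a separate clinical matter, not addressed here.
- **Section 10.1.1:** state that tables by relationship show drug-related, SBRT-related and related-to-either events, and that the last is what the report calls treatment-related.
- **Section 9.2 recording table:** state that the collect-all rule of Section 9, which is equivalent to the table's Phase I entries, applies to all patients.

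The cost is one extra field on the adverse-event form and some table wording. Treatment-related rates in groups 2 and 3 may look slightly higher than on a drug-only code.
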